The barrier to increasing access to this form of contraception is the training required to safely administer the implants. Currently, subcutaneous contraceptive implants are inserted free-hand by trained healthcare providers. This requires healthcare providers to precisely thread a large bore needle just beneath the skin along the underside of a woman's arm to deploy the implant (Inc., n.d.; Levine, Sinofsky, & Christ, 2008). If performed correctly, the contraceptive implant is left above the subcutaneous fat layer, just beneath the skin (Figure 1a). However, this freehand method can lead to implants being inserted too deeply, in the fat layer or embedded in the muscle (Figure 1b). In these cases, physicians must use high-frequency ultrasound, MRIs, and surgical techniques to remove these deeply embedded implants, leading to higher costs, participant discomfort, and higher risk of complications/infections (Evans, Holman, & Lindsay, 2005; Gurel et al., 2012; Mansour et al., 2008; Merki-feld, Brekenfeld, Migge, & Keller, 2001; Nelson & Sinow, 1998; Singh, Mansour, & Richardson, 2006). Due to these complications, the World Health Organization recommends that only specially trained providers administer contraceptive implants; significantly limiting their availability in rural areas (World Health Organisation, 2012). Our research team has developed the SubQ Assist, a task-shifting device that facilitates the consistent and accurate administration of contraceptive implants

thereby eliminating complications during removal and allowing community healthcare workers to provide safe access in rural areas.

[figure not shown]
The SubQ Assist Implant Insertion Device (Figure 1) was co-created by engineering students and clinicians at the University of Michigan (Ann Arbor) and St. Paul's Hospital (Addis Ababa). The initial need for the device was first identified through extensive ethnographic fieldwork performed during August 2013 which included observations and interviews with over 35 healthcare providers

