(from community health workers to hospital provosts), family planning NGOs, and ministry of health officials. Subsequent designs were then refined through further fieldwork during May 2014, January 2015, and June 2016. In total, we have performed over 200 hours of observations, interviews with more than 110 stakeholders, and have conducted usability tests with 130 healthcare providers in Ethiopia (Mohedas, Daly, & Sienko, 2015). This process has allowed our team to align the design requirements of the SubQ Assist with an established need of the Ethiopian Ministry of Health, meet the requirements of our end-users, and develop our device to meet the regulatory requirements in Ethiopia.

[figure not shown]
Figure 1: Current design of the SubQ Assist showing the top and bottom views of the device.

The SubQ Assist Implant Insertion Devicewas designed to eliminate the risk of improper insertions regardless of the training level of the healthcare provider. The SubQ Assist is clipped to any standard blood pressure cuff and wrapped around the participant's upper arm. Inflating the cuff to 40 mmHg pushes the skin and subcutaneous tissue into the device's cavity (Figure 2). The guide on the front of the device can then be used to both administer the anesthetic and guide the implant needle just under the skin. In doing so, the SubQ Assist ensures that the implant is administered just beneath the skin and above the subcutaneous fat. This accurate insertion allows for easy removal when the implant needs to be replaced. After deploying the implant, the implant needle, anesthetic needle, and the SubQ Assist are disposed of (fitting the current healthcare environment in rural settings). The efficacy of the SubQ Assist (as measured by the depth accuracy of insertions) has been tested on simulators showing

that a minimally trained provider increases accuracy of insertion by ~83% when using the SubQ Assist as compared to traditional free-hand insertion (Mohedas, Sarvestani, et al., 2015). Additionally, the SubQ Assist has been validated through cadaver testing confirming the accuracy of the insertion and the blood pressure insertion methodology.

Figure 2: Mechanism demonstrating how the SubQ Assist works and how it ensures accurate administration.

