Development of the SubQ Assist Implant Insertion Device would dramatically reduce the training barriers to accessing long-acting contraceptive implants. It would enable Ministries of Health in low- and middle-income countries to enable their community healthcare workers (who are readily accessible in rural areas) to administer these implants safely and effectively. This would open up a long-acting contraceptive option to a population of women who are currently underserved and have little access to modern contraception. Based on our analysis of United Nations Data on contraceptive implant use, we estimate that implementation of the SubQ Assist Implant Insertion Device in Ethiopia, Ghana, Kenya, and Uganda would lead to ~750,000 women receiving implants in underserved, rural areas (that currently have limited access. The study below will form the basis for clinical data needed to prove the safety and efficacy of the device.

Research Study

To date, we have performed simulator testing and cadaver testing to assess the efficacy of the SubQ Assist Implant Insertion Device. A trial to assess the safety and efficacy in human subjects is now needed to fully understand how effective the SubQ Assist is with respect to administering contraceptive implants. The study proposed below will allow us to understand whether the SubQ Assist is safe and can effectively place implants just under the skin in the subcutaneous layer.

Objective

The objective of this study is assess the safety and efficacy of the SubQ Assist device.

Specific Aims

SP1: Assess how soft tissue physically behaves when pressurized by the SubQ Assist Implant Insertion Device via a blood pressure cuff.

SP2: Determine the efficacy of the SubQ Assist Implant Insertion Device by measuring the depth of a placebo implant via ultrasound.

SP3: Identify any side effects associated with use of the SubQ Assist as compared to those associated with traditional standard insertion.

Arm 1: Methodology

One factor that may negatively affect the accuracy of the SubQ Assist Implant Insertion Device is the compression of the soft tissue and skin when the blood pressure cuff is inflated around the upper arm. To investigate this, we will be taking Magnetic Resonance Images of the SubQ Assist device inflated around the arm of participants in this arm of the study.

Arm 1: Inclusion Criteria

- 1. Healthy adults ages 18 to 49
- 2. Ability to understand study procedure and informed consent document

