- 3. Participants who agree to participate will then be given the informed consent document to review with the physician. The physician will walk the participants through the document and provide the opportunity for the participant to ask any questions.
- 4. After signing the informed consent, a researcher will then collect background information on the participant including:
 - a. Height
 - b. Weight
 - c. Arm circumference
 - d. Age
- 5. Placebo implants will then be inserted by a trained physician using the SubQ Assist (See Appendix A for the insertion procedure). The device used in the trial will be 3D printed using biocompatible Class I resins. Each device will be sterilized using an autoclave prior to the procedure. Appendix B Provides more details with respect to the process of manufacturing and sterilizing the SubQ Assist. The placebo implants will be made by Albright Technologies (an ISO 13485 certified producer of medical devices).
- 6. The physician will use sterile gloves throughout the procedure. Iodine is used to disinfect the area where the SubQ Assist will come into contact with the participant and where the insertion will occur.
- 7. Lidocaine will be used as local anesthetic along the implant trajectory.
- 8. After administration the following measurements will be made:
 - a. Implant palpability: Can the implant be easily palpated through the skin and, if so, can the entire implant be palpated.

- b. Visibility: Can the implant impression be seen when the arm is in a relaxed position?
- c. Ultrasound measurement: Ultrasound images of the embedded implant will be taken (which will allow for post-processing to capture the depth of the individual implant).
 - i. A research assistant/co-investigator with expertise in ultrasound imaging will administer the ultrasound (Logiq V2 2016 by GE). A 10-15 MHz ultrasound with linear array and 50mm footprint will be used. The ultrasound will be set to superficial focus (<3cm).
 - 1. Two transverse images will be taken: at the distal and at the proximal ends of the implant.
 - 2. A third ultrasound image will be taken in the longitudinal direction.
- d. Bruising/Bleeding: Notes will be taken on whether any bruising/bleeding is occurring and, if so, how much. Sterile gauze will be used to assess the amount of blood loss (comparing pre- and post-procedure gauze weight to assess amount of blood loss).

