members will monitor participants during the study to assess whether participation in the study needs to end prematurely.

Arm 1: Data Analysis

MRI scans will be taken at multiple pressures and with a diversity of subjects (with respect to their BMI and arm circumference). MRI scans will allow us to evaluate the level of compression of the muscle, subcutaneous fat, and skin when the SubQ Assist Implant Insertion device is pressed again the participant's upper arm when the blood pressure cuff is inflated at various pressures.

Arm 2: Data Analysis

Data collected will include a range of measurements. The key data will be derived from the ultrasound images, namely: distal end depth (mm), proximal end depth (mm), implant depth angle (degrees), and average implant depth (mm). We will assess the depth of implants embedded using the SubQ Assist procedure and comparing this with the data currently available in the literature. We will be looking to assess if there is any difference between the implant depth measurements obtained in this study and the recommended depth of implant by the manufacture and those measurements found in the literature.

Adverse Events

Adverse events will be recorded from the time of consent until the final visit. Adverse events that are observed by the investigator or reported by the subject should be recorded on the CRFs. For all adverse events and complications, a description of the event, date first observed, any action taken, and ultimate outcome will be recorded.

For all adverse effects, sufficient information will be pursued and/or obtained so as to permit 1) an adequate determination of the outcome of the effect (i.e., whether the effect should be classified as a serious adverse effect) and; 2) an assessment of the causal relationship between the adverse effect and the investigational device or, if applicable, the other study treatment or diagnostic product(s).

Adverse effects felt to be associated with the investigational device or, if applicable, other study treatment or diagnostic product(s) will be followed until the effect (or its sequelae) or the abnormal test finding resolves or stabilizes.

[figure not shown]
All adverse events and complications should be documented on the CRFs and tabulated for reporting as required according to the FDA and IRB reporting guidelines.

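### The Arm 2 efficacy question asks only whether depths differ from a reference; a negative answer would neither show agreement nor count the implants placed too deep

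*Protocol*

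**What the plan says.** The Background of the Protocol explains the problem with current practice: "this freehand method can lead to implants being inserted too deeply, in the fat layer or embedded in the muscle". It then says that the device "ensures that the implant is administered just beneath the skin and above the subcutaneous fat". The Research Study section asks whether the device "can effectively place implants just under the skin in the subcutaneous layer", and aim SP2 is to "Determine the efficacy of the SubQ Assist Implant Insertion Device by measuring the depth of a placebo implant via ultrasound".

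Arm 2: Data Analysis lists the key variables as depth at each end, depth angle and average depth. It continues: "We will assess the depth of implants embedded using the SubQ Assist procedure and comparing this with the data currently available in the literature". The question to be answered is then stated: "We will be looking to assess if there is any difference between the implant depth measurements obtained in this study and the recommended depth" (the manufacturer's), and likewise the literature depths. No value in mm is given for the recommended depth, and the Protocol does not say whether it is an upper limit, a range or a target.

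The measurements come from ultrasound. In Arm 2: Insertion Protocol the images are ones "which will allow for post-processing to capture the depth of the individual implant", and "Two transverse images will be taken: at the distal and at the proximal ends of the implant".

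**The concern.** The aim concerns where implants end up, and the one placement failure described is an implant that is too deep. The analysis sentence asks something looser: whether the measured depths and a reference differ. Two difficulties follow.

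- Absence of a detected difference is not evidence of agreement. It may reflect wide spread or a small sample.
- A comparison of averages would satisfy the sentence, and an average can sit on the reference while individual implants lie well below it.

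This is the only efficacy comparison stated for SP2. The study could report a result that follows the Protocol to the letter without saying how many participants had an implant deeper than recommended. The literature comparison has a further weakness: the study has no concurrent freehand group. If the published depths come from freehand insertions, a better device ought to differ from them, so the wording does not even say which answer would be favourable.

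**Working it through.** **Inputs.** n = 50 participants, single arm (Arm 2: Methodology). The Protocol states no test, significance level, standard deviation (SD), margin or success criterion, so there is no plan figure to reproduce. Where a test is needed below, I assume a two-sided 5% one-sample t-test of mean depth with normally distributed depths. That is an illustration, not the Protocol's method.

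**1. What a no-difference result on the mean would allow.** The test is non-significant when the observed mean lies within t(0.975, 49)/√50 = 2.0096/7.0711 = 0.284 SD of the reference. Taking the observed mean and SD as the true ones, the share of implants deeper than the reference is Φ(d), where d is the mean's distance on the deep side in SD units:

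- d = −0.284: about 39%
- d = 0: 50%
- d = +0.284: about 61%

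These shares matter if the recommended depth is an upper limit. If it is a target with a tolerance, and the mean is exactly on target, the share too deep is 1 − Φ(tolerance/SD):

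| SD ÷ tolerance | Share too deep |
|---|---|
| 0.5 | 2.3% |
| 0.75 | 9.1% |
| 1 | 15.9% |

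In all three rows the test shows no difference about 95% of the time. The same answer therefore covers very different misplacement rates.

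**2. What a count would show at n = 50.** Exact (Clopper-Pearson) two-sided 95% intervals, with lower limit Beta(0.025; x, n − x + 1) and upper limit Beta(0.975; x + 1, n − x):

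| Correctly placed | 95% interval |
|---|---|
| 50/50 | 92.9% to 100% |
| 48/50 | 86.3% to 99.5% |
| 45/50 | 78.2% to 96.7% |

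The chance of seeing at least one too-deep case is 1 − (1 − p)^50: 63.6% if p = 2%, 92.3% if p = 5%, 99.5% if p = 10%. The count is informative at the planned size.

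**3. Precision given up.** The 95% interval for mean depth has half-width 0.284 SD. The interval for 48/50 spans 99.5 − 86.3 = 13.2 percentage points. The proportion is the coarser summary, so it should accompany the mean and not displace it.

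**4. Why the unit must be settled.** Arm 2: Risks to Participants speaks of a single placebo implant, while step 12 of Appendix A describes placing one in a second direction. With a too-deep rate q per implant and two implants, the participant-level rate runs from q (fully dependent) to 1 − (1 − q)² (independent):

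- q = 2%: 2% to 1 − 0.98² = 4.0%
- q = 5%: 5% to 1 − 0.95² = 9.8%

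The reported proportion could nearly double on this point alone.

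**The case against.** The case on the other side is substantial in four respects.

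- **Direction.** A reader might infer that the planned comparison cannot tell shallower from deeper. The documents do not support that. The key data are depths in mm, and a difference in mm has a sign. Direction is lost only if a bare yes/no conclusion is reported, which the Protocol does not say it will do.
- **Two-sidedness.** A reader might also infer that a two-directional comparison is wrong because too-deep placement is the only placement harm named. The Background, when describing the simulator work, treats efficacy as accuracy of depth, and accuracy can fail in either direction. The looser question fits that notion.
- **Method.** No test of the mean is specified, and the sentence could be carried out implant by implant. The misplacement rates in step 1 belong to an assumed model and are not properties of this trial.
- **Data.** Depth at both ends, palpability and visibility are all to be recorded, so nothing prevents a count of deep implants.

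These points narrow the criticism but do not remove it. It can also be said that tests and thresholds belong in a statistical analysis plan. That is true of tests and thresholds, but here the Protocol itself states the question, and an analysis plan that followed it faithfully could stop at a comparison of averages. Replacing the depth summaries with a binary main result would be partly a matter of preference, and is not asked for here.

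**Conclusion.** The stated Arm 2 question does not match the Protocol's own aim closely enough. A finding of no difference would not show agreement with the recommended depth and would leave the number of too-deep implants unstated. This conclusion rests on the wording alone; it needs neither the t-test nor the normal model.

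The size cannot be given as a trial-specific error rate, because the recommended depth, its nature and the spread of depths are not in the document. What can be said is that 50 participants suffice for a useful count, with 48/50 giving 86.3% to 99.5%. The measurements are sound, nothing is lost, and the defect can be repaired by rewording before data are seen.

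**What to change.** In Arm 2: Data Analysis:

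1. Keep the depth and angle summaries. Report the signed difference in mm between measured and recommended depth with a 95% confidence interval, in place of a conclusion of difference or no difference.
2. Add the number and proportion of participants with any implant end deeper than the manufacturer's recommended depth (or outside its range), with an exact two-sided 95% interval.
3. Before data are seen, cite the recommended depth in mm and say whether it is a limit, a range or a target; if a target, give the tolerance.
4. Treat the literature comparison as descriptive.

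Two inconsistencies must be reconciled by the sponsor. The single implant in Arm 2: Risks to Participants conflicts with Appendix A, step 12, and this decides the unit of analysis. The placement described in the Background ("ensures that the implant is administered just beneath the skin and above the subcutaneous fat") does not match the Research Study wording ("can effectively place implants just under the skin in the subcutaneous layer"), and this decides what correct placement means.

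**Cost.** If one implant is inserted, no new measurements are needed. If two are, the listed ultrasound images must cover each. The sponsor has to commit to a threshold in advance, and the proportion is less precise than the mean. A pass/fail minimum is not required, so the fix does not reopen the sample size.

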Appendix A

[figure not shown]
Below we have a detailed discussion of how the SubQ Assist Implant Insertion Device is used to insert the placebo implants:

- 1. A sterile drape is first draped underneath the upper arm of the participant and a sterile field is created.
- 2. An insertion mark is made at 6-8cm above the epicondyle.
- 3. Iodine is used to disinfect the area where the SubQ Assist will come into contact with the participant and where the insertion will occur.
- 4. The SubQ Assist is removed from its sterile packaging and clipped onto the blood pressure cuff (Step 1 below).
- 5. The blood pressure cuff is wrapped around the participant's upper arm aligning the device with the insertion site mark (Step 2 below).
- 6. Once secured, the blood pressure cuff is inflated to ~40mm Hg (Step 3 below). This pushes the skin and subcutaneous tissue into the cavity on the underside of the SubQ Assist.
- 7. The lidocaine is then inserted through the guide on the front of the device; placing the local anesthetic along the implant trajectory.
- 8. The cuff is deflated while the lidocaine takes effect.
- 9. The cuff is re-inflated after a two minute waiting period to ~40mm Hg.
- 10. The implant trocar is removed from its sterile packaging and inserted through the guide of the SubQ Assist (Step 4 below).
- 11. The plunger is removed and the sterile placebo implant is removed from its packaging and inserted into the trocar. The plunger is inserted until resistance is felt, the trocar is then pulled back until it touches the plunger.
- 12. The trocar is rotated to insert an implant in the second directions.
- 13. The trocar is removed completely, the cuff is deflated and removed from the patients arm.
- 14. The insertion site is cleaned and a steristrip is applied.

Step 4

Step 5

Step 6

Appendix B

The 3D printed prototypes used in this study will be made using a Formlabs Form 2 printer (https://formlabs.com/3d-printers/form-2/). This printer allows us to manufacture highly accurate (resolution levels of 25 microns) prototypes that will be dimensionally equivalent to the device that would eventually be produced using injection molding and have similar material properties to common biocompatible plastics used within the medical industry. As the SubQ Assist functions almost exclusively based on its geometry and physical characteristics, we believe that the 3D printed devices we are able to produce provide a sufficient similarity to what would be produced at scale during injection molding.

The devices produced will be made from a specific resin used in the 3D printer that is an autoclavable, Class 1 biocompatible resin. This has been extensively used to create surgical guides within dentistry. The ability to autoclave the material (without dimensional deformation) will allow us to create sterile, ready to use devices that minimize the risk of injections occurring at the insertion site.

The material is certified and in compliance with the following standards:

- EN-ISO 10993-1:2009/AC:2010: non-mutagenic, non-cytotoxic, not induce any erythema or edema reactions, not a sensitizer, not cause systemic toxicity
- EN-ISO 20795-1:2013 (Dentistry Base Polymers Part 1: Denture Base Polymers)
- EN-ISO 7405:2009/A1:2013 (Dentistry Evaluation of biocompatibility of medical devices used in dentistry)
- EN-ISO 10993-1:2009/AC:2010 (Biological evaluation of medical devices)

Appendix C

Arm 2: Follow-up phone call / questionnaire:

- 1. On a scale of 1 to 10, what pain do you currently feel in your upper arm?
- 2. Is there any bruising on your upper arm?
- 3. Has there been any fluid draining from the incision?
- 4. Has there been any redness or swelling of the insertion site?
- 5. Has there been any bleeding from the insertion site?

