- 1. Participants will be called or emailed (depending on their preference) one week after the insertion procedure to assess any pain or discomfort associated with the insertion protocol.
- 2. The questions outline in Appendix C will be asked of all participants.
- 3. Any adverse events will be recorded

Arm 2: Follow-up Visit Protocol (3 weeks ± 1 week)

- 1. Participants will return for a follow-up visit three weeks after the insertion procedure (± 1 week).
- 2. During this visit, the incision will be checked for safe healing and infection. Photographs will again be taken of the insertion site to assess potential bruising. Photographs will not be identifiable (consist of upper arm only). Any adverse events will be recorded.

Arm 2: Placebo Implants

The placebo implants used in this study will be manufactured by Albright Technologies Inc (https://albrightsilicone.com). The placebo implant is made to the same specifications as the contraceptive implants with respect to both geometry and material characteristics. The implants are made from short-term implantable silicone which is a grade of silicone that can be implanted in the body for 29 days or less. Manufacturing will be done in a class ISO 7 compliant controlled environment room. Parts will be sterilized and packaged sterile allowing the research team to use a disposable sterile implants for each research participant.

Arm 2: Risks to Participants

The participants in this study will be healthy adults [18-49 years of age]. They will receive a placebo implant (using the SubQ Assist), additional measurements, implant removal, a follow-up check-in, and a follow-up visit.

Participants in this study will be receiving placebo implants. There is no anticipated risk of a decrease in cognitive function during the study and participants will be allowed to withdraw from the study at any time. There is a highly unlikely risk of a reaction to the lidocaine local anesthetic that could occur. A strong reaction would result in the participant being prematurely withdrawn from the study. To minimize this risk, participants will be asked about any prior reactions to anesthesia they may have had in the past during recruitment. Placebo implants will be made of implantable grade silicon (See Appendix D). We will therefore ask participants about potential silicone allergies prior to enrollment in the study. Study

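### The day-7 contact is meant to assess any pain from the insertion protocol, but its only pain question covers pain felt at that moment, so pain that has already resolved is not systematically asked about

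*Protocol*

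**What the plan says.** Under Arm 2: Follow-up Check-in (7 days), the purpose of the contact is stated as an approach to participants "one week after the insertion procedure to assess any pain or discomfort associated with the insertion protocol". It is made by phone or email as the participant prefers, and "The questions outline in Appendix C will be asked of all participants".

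Appendix C has five questions. Question 1 is the only one on pain: "On a scale of 1 to 10, what pain do you currently feel in your upper arm". Question 2 is also in the present tense: "Is there any bruising on your upper arm". Questions 3 to 5, on drainage, redness or swelling, and bleeding, ask whether these have happened at all since the procedure.

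The other Arm 2 contacts are the insertion day and the visit at 3 weeks ± 1 week. At that visit, "During this visit, the incision will be checked for safe healing and infection" and "Photographs will again be taken of the insertion site to assess potential bruising". At both follow-up contacts, "Any adverse events will be recorded".

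SP3, under Specific Aims, is to identify side effects of using the device compared with standard insertion.

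**The concern.** The stated purpose covers any pain or discomfort tied to the insertion protocol, while the question covers only what is felt when the call or email is answered. Someone with marked pain at insertion and for a few days afterwards, but none at day 7, gives the same answer as someone who never had pain.

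The scale adds a smaller difficulty. It starts at 1 and has no written anchors, so a score of 1 can mean no pain or slight pain. A caller could explain this, but the protocol contains no explanation, and some participants will answer by email.

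Transient pain is a foreseeable effect of trocar insertion and of removal through the same incision, and it belongs among the side effects SP3 is meant to identify. If it is not asked for, its recorded frequency and severity will depend on who happens to mention it.

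**Working it through.** No formula applies. The check is whether any Arm 2 step asks the participant about pain over a period other than the moment of the day-7 contact.

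1. **Insertion day, step 8 of the Insertion Protocol.** There are six items, a to f: palpability, visibility, ultrasound, bruising and bleeding, photograph, and a physician case report. Items that ask the participant about pain: 0 of 6.

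2. **The physician report, step 8f.** It has six prompts: attaching and wrapping the device, inflating the cuff, giving lidocaine, inserting the trocar, inserting the implant, and taking off the device. Pain at insertion could be noted here as an issue, but the respondent is the physician. Prompts about implant removal: 0 of 6. Removal is step 9, after the step 8 measurements are complete.

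3. **Removal, steps 9 to 11.** Extra anesthetic may be given, and the need for it might prompt an informal question about pain. No participant rating is called for.

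4. **Wound-care advice, step 12d.** Participants are told to contact the team or their own doctor about signs of infection. The list includes increasing pain and other discomfort at the incision. This prompts a report in the days before day 7, but it is neither a question put to everyone nor tied to a scale.

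5. **Day 7, Appendix C.** Pain questions: 1 of 5, for the present moment only. By tense, questions 1 and 2 are present (2 of 5) and questions 3 to 5 look back (3 of 5).

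6. **Visit at 3 weeks ± 1 week.** Healing, infection, photographs and adverse events. Pain questions: 0.

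7. **Adverse Events section.** Events observed by the investigator or reported by the subject are recorded from consent to the final visit. Pain can enter by this route, without a set question or scale.

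In total, 1 of 3 scheduled Arm 2 contacts asks the participant about pain. For comparison, the Arm 1 risk section has participants asked about discomfort after each trial, although no implant is inserted in that arm.

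Pain that has resolved by day 7 thus has three routes into the record: adverse-event recording, the step 8f report, and a contact made under step 12d. None of them is a question put to every participant.

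**The case against.** **The purpose can be read more narrowly.** It could mean pain still present at one week, which question 1 does measure. The present tense may be deliberate, since pain persisting to day 7 may signal a complication, whereas drainage and bleeding are events. This reading cannot be excluded, so the mismatch is not an outright contradiction. It fits poorly, though, with the word any in the stated purpose and with the look-back form of questions 3 to 5. Even if it is accepted, resolved pain remains unasked for an aim concerned with side effects.

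**Other routes exist.** A reader might infer that pain resolved before day 7 is lost altogether. The protocol does not support that. Adverse events are recorded throughout, study members monitor participants, and step 12d invites reports of worsening pain or other discomfort. What stands is that these routes are not systematic, and that pain which did not worsen is the most likely to go unreported.

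**Pain is not key data.** The Arm 2 data analysis names ultrasound depth and angle as key. That limits the weight of the point, but SP3 is still one of three stated aims.

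**The scale.** One is the evident floor of a 1 to 10 scale, and no stated analysis depends on separating no pain from slight pain. The ambiguity affects only the lowest score and matters mainly for email replies. It supports written anchors and little more.

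**Bruising.** The present tense of question 2 might suggest an equal gap for bruising. It does not. Bruising is noted and photographed on the insertion day and photographed again at the later visit. Only bruising that appears after step 8 and clears before day 7 is not asked about.

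**Conclusion.** The concern holds in a limited form. The only pain question in Arm 2 is narrower than the purpose the protocol gives for the contact, and pain that has resolved by day 7 is not systematically asked about. Pain data for SP3 will tend to be incomplete.

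The size of the shortfall cannot be estimated, because the protocol gives no expected pain frequency, duration or reporting rate. A reader might go further and infer that the comparison with standard insertion will be biased in favor of the device. The protocol does not support that either, because it does not say how pain was measured in the comparison data. If those data came from a similarly narrow question, the shortfall could be common to both sides.

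The conclusion assumes that Appendix C is used as written and that callers add no look-back questions of their own. The change is worth making because it costs almost nothing and alters what is recorded.

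**What to change.** In Appendix C, keep current pain and add three look-back items: worst pain during insertion, worst pain during implant removal, and worst pain in the days since. Put all four on one scale with written anchors, including the value for no pain, and use identical wording for phone and email.

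Insertion and removal should be asked about separately. The implant comes out the same day, sometimes through an enlarged incision, so a single score for worst pain since the procedure would mix removal pain with insertion pain, and SP3 concerns insertion.

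Optionally, take a brief participant rating on the insertion day, after insertion and before removal, so that insertion pain is recorded separately at the time. Rewording question 2 to look back is also optional and minor.

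The cost is three extra questions in a contact already scheduled, and one more at an existing visit if the optional rating is used. The drawbacks are one-week recall, insertion-day ratings given under lidocaine, and somewhat higher reported pain rates, which should be kept in mind when comparing with sources that asked less.
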